6.0 ANALYSIS ENDPOINTS

6.1 Primary Endpoints

Primary endpoints for the study include:

- Percentage of subjects who experience at least 1 treatment emergent adverse event (TEAE).
- Percentage of subjects who meet the markedly abnormal criteria for clinical safety laboratory tests at least once postdose.
- Percentage of subjects who meet the markedly abnormal criteria for vital sign measurements at least once post dose.
- Percentage of subjects who meet the markedly abnormal criteria for 12-lead safety electrocardiogram (ECG) parameters at least once post dose.

6.2 Secondary Endpoints

Plasma PK Parameters of TAK-831:

1. Maximum observed plasma concentration (C_{max}) (Day 1).
2. Maximum observed steady-state plasma concentration during a dosing interval (Day 16).
3. Time of first occurrence of C_{max} (Days 1 and 16).
4. Area under the plasma concentration-time curve during a dosing interval (Days 1 and 16).

6.3 Additional Endpoints

CCI

CCI

7.0 DETERMINATION OF SAMPLE SIZE

The sample size chosen of 8 subjects for all Cohorts (6 active : 2 placebo) is considered to be sufficient for evaluation of safety, tolerability, and PK of each cohort to determine the dose for the next cohort. The sample size was not based on statistical power considerations.

8.0 METHODS OF ANALYSIS AND PRESENTATION

8.1 General Principles

All study-related raw and derived data for randomized subjects will be presented in listings by cohort. Randomized subjects are the subjects who are enrolled and received a randomization number.

Continuous data will be summarized using the following descriptive statistics: number of subjects (N), mean, standard deviation (SD), median, minimum, and maximum, where appropriate. Where indicated, the coefficient of variation (%CV) and geometric mean will also be included in the summary of continuous data. Categorical data will be summarized using the number and percent of subjects for each category, where appropriate.

Unless otherwise stated, baseline is defined as the last observed value before the first dose of study medication.

As applicable, summaries will be presented by pooled placebo, each combination of TAK-831 dose level /formulation, TAK-831 overall and overall.

All data analyses and figures will be generated using SAS System® Version 9.2 or higher.

8.1.1 Study Definitions

There are no study-specific definitions.

8.1.2 Definition of Study Days

Study day will be calculated relative to the date of the first dose of the study drug in each study part. Study days prior to the first dose of study drug in each study part will be calculated as: {date of assessment/event – date of first dose of study drug of the subject}. Study days on or after the first dose of study drug will be calculated as: {date of assessment/event – date of first dose of study drug of the subject + 1}.

8.1.3 Definition of Study Visit Windows

There will be no visit windows.

8.1.4 Conventions for Missing Adverse Event Dates

There will be no imputation of incomplete or missing adverse event dates.

8.1.5 Conventions for Missing Concomitant Medication Dates

There will be no imputation of incomplete or missing concomitant medication dates.

8.1.6 Conventions for Missing Data

There will be no imputation of incomplete or missing data.

Plasma or CSF concentrations that are below the limit of quantification (BLQ) will be treated as zero in the summarization of concentration values and derivation of PK parameters. These values will be flagged in the data listings and deviations from this convention may be considered on a case-by-case basis as deemed appropriate.

8.2 Analysis Sets

Safety Set

The Safety Set will include all randomized subjects who receive at least 1 dose of study drug in a given part of the study. Subjects in this set will be used for demographic and safety summaries.

Pharmacokinetic Set

The PK set will include all randomized subjects with at least 1 measurable concentration for TAK-831. All subjects with valid PK parameter estimates will be included in the summaries and analyses for that parameter.

Pharmacodynamic Set

CCI

If any subject is found to be noncompliant with the dosing schedule or has incomplete data, a decision will be made on a case-by-case basis as to whether that subject should be included in the PK and PD analyses; however, data for all subjects will be presented in the data listings.

8.3 Disposition of Subjects

Disposition of all screened subjects (denominator) will be tabulated (count and percent); there will be no inferential analysis of subject disposition data.

Summaries will be presented by pooled placebo, each combination of TAK-831 dose level/formulation, TAK-831 overall and overall.

Disposition of all randomized subjects will be tabulated for each part of the study:

- All subjects received at least one dose of study drug (denominator).
- Subjects who completed the study.
- Subjects who prematurely discontinued study.

Primary reasons for discontinuation of study, as entered on the electronic case report form (eCRF), will be tabulated. Reasons for discontinuation include adverse event, significant protocol deviation, lost to follow-up, withdrawal by subject, study termination, and other. The date of first dose, date of last dose, duration of treatment and the reason for premature discontinuation of study drug/study visit will be presented for each subject in listings.

Disposition of screen failure subjects will be summarized descriptively. Primary reasons for failure will be summarized and will be presented in a data listing.

8.4 Demographic and Other Baseline Characteristics

Demographic and baseline characteristics will be summarized using the Safety Set. Summaries will be presented by pooled placebo, each combination of TAK-831 dose level and formulation, TAK-831 overall and overall.

Summary statistics will be presented for continuous variables (age, height, weight, and body mass index [BMI]). The number and percentage subjects within each category will be presented for categorical variables (for example, gender, race, etc.). Individual subject demographic and baseline characteristic data will be listed.

Demographic variables of screen failure subjects and reasons for screen failures will be summarized overall for subjects who are screened but not enrolled in the study.

8.5 Medical History and Concurrent Medical Conditions

Medical history and concurrent medical conditions will be coded using the Medical Dictionary for Drug Regulatory Activities (MedDRA, version 18 or higher) coding system.

Medical history includes any significant conditions or diseases relevant to the disease under study that stopped at or prior to signing of informed consent. Ongoing conditions are considered concurrent medical conditions.

All medical history and concurrent medical condition data will be listed by site (study center) and subject number. The listing will contain subject identifier, treatment, system organ class (SOC), preferred term (PT), whether there was any medical history or concurrent condition, and, if yes, a detail of the medical history or concurrent condition. No inferential statistics will be presented.

8.6 Medication History and Concomitant Medications

Medication history information includes any medication relevant to eligibility criteria stopped at or within 28 days prior to signing of informed consent. Concomitant medications are recorded on the eCRF and include any medications, other than study drug, taken at any time between informed consent and the end of the study.

All medication history and concomitant medications will be listed by site (study center) and subject number. The listings will contain subject identifier, treatment, World Health Organization Drug Dictionary (WHODrug) preferred medication name, dose, unit, frequency, route, start date, stop date, whether the medication was ongoing, and reason for use. No inferential statistics will be presented.

Medication history and concomitant medications will be coded using the WHODrug Version 01March 2017 or higher.

8.7 Study Drug Exposure and Compliance

The date and time of each dose for each subject will be reported in the data listing for all subjects. Meal consumptions and timing will be reported in the data listing as well. Summaries

of PK data will be provided by dose and formulation group. No other summary statistics for the extent of exposure to study drug or compliance calculations will be performed for this study.

8.8 Efficacy Analysis

Not applicable.

8.9 Pharmacokinetic/Pharmacodynamic Analysis

8.9.1 Pharmacokinetic Analysis

All PK summaries and analyses will be based on the PK set. PK parameters of TAK-831 will be derived using non-compartmental analysis methods. The PK parameters of TAK-831 will be determined from the concentration-time data for all evaluable subjects. Actual sampling times, rather than scheduled sampling times, will be used in all computations involving sampling times.

Serial blood samples for determination of TAK-831 concentrations will be collected on Day 1 (within 30 minutes before dosing) and at 0.5, 1, 1.5, 2, 4, 8, 12, 24, hours after the morning dose; on Day 10 (predose), Day 13 (predose), and on Day 16 at predose (within 30 minutes before dosing), and at 0.5, 1, 2, 4, 8, 12, 16, and 24 hours after the morning dose and at Early Termination.

In CSF cohorts, serial CSF samples will be collected On Day 1 and/or Day 16 at predose (within 30 minutes before dosing) and at 1, 4, 8, 12, and 24 hours after the morning dose.

The following pharmacokinetic parameters will be calculated for plasma (Day -1, Day 1 and Day 16) and CSF (Days 1 and/or 16) concentrations of TAK-831 when appropriate:

Symbol/Term	Definition
$AUC_{\tau} / AUC_{\tau, CSF}$	Area under the concentration-time curve during a dosing interval.
$AUC_t / AUC_{t, CSF}$	Area under the concentration-time curve from time 0 to time t. (Day 1 only)
AUC_{∞}	Area under the concentration-time curve from time 0 to infinity, calculated using the observed value of the last quantifiable concentration (Day 1 only)
$R_{ac(AUC)} / R_{ac(AUC, CSF)}$	Accumulation ratio based on AUC_{τ} .
$R_{ac(C_{max})} / R_{ac(C_{max}, CSF)}$	Accumulation factor based on C_{max} .
$C_{av,ss} / C_{av,ss, CSF}$	Average concentration during a dosing interval, at steady state.
$C_{max} / C_{max, CSF}$	Maximum observed concentration on Day 1 and Day 16.
CL/F	Apparent clearance after extravascular administration, calculated as $=Dose/AUC_{\infty}$ after a single dose. Plasma only. (Day 1 only)
λ_z	Terminal disposition phase rate constant. Plasma only.
$t_{1/2z}$	Terminal disposition phase half-life. Plasma only.
$t_{max} / t_{max, CSF}$	Time of first occurrence of C_{max} .
V_z / F	Apparent volume of distribution during the terminal disposition phase after extravascular administration, calculated using the observed value of the last quantifiable concentration. Plasma only. (Day 1 only)

Descriptive statistics (N, arithmetic mean, SD, %CV, median, minimum, and maximum) will be used to summarize the plasma and CSF PK parameters for TAK-831, including dose-normalized C_{max} and AUCs, by dose and formulation. In addition, geometric mean will be computed for C_{max} and AUCs, including those dose-normalized C_{max} and AUCs. Individual plasma PK parameters will be presented in a data listing.

Dose proportionality in plasma and CSF PK parameters (C_{max} and AUCs as well as dose-normalized C_{max} and AUCs) will be assessed graphically using box-plots for Day 1 and Day 16 plasma and CSF PK parameters for each formulation. Other figures needed for PK data are described in Clinical pharmacology Analysis Plan for this study.

Additional analyses will be included if appropriate.

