# 7.6 Procedures for Discontinuation or Withdrawal of a Subject

The investigator may discontinue a subject's study participation at any time during the study when the subject meets the study termination criteria described in Section 6.5.5. In addition, a subject may discontinue his or her participation without giving a reason at any time during the study. Should a subject's participation be discontinued, the primary criterion for termination must be recorded by the investigator. In addition, efforts should be made to perform all procedures scheduled for the Early Termination Visit. Discontinued or withdrawn subjects may be replaced to ensure that a minimum of 6 subjects are completed for each cohort. This will be examined by the team on a case-by-case basis.

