# 11.1.3 PK Analysis

Concentrations of TAK-831 in plasma (all cohorts) and CSF (CSF Cohort[s]) will be summarized by dose, drug formulation, and day over each scheduled sampling time using descriptive statistics. Individual plasma concentration data versus time will be presented in a data listing.

PK parameters of TAK-831 will be derived using noncompartmental analysis methods. The PK parameters of TAK-831 will be determined from the concentration-time data for all evaluable subjects. Actual sampling times, rather than scheduled sampling times, will be used in all computations involving sampling times. Plasma and CSF PK parameters, including dose-normalized Cmax and AUCs, will be summarized by dose, drug formulation, and day using descriptive statistics. Changes in the PK parameters from Day 1 to Day 16 will be assessed by summarizing the ratio of Day 16 to Day 1 by dose and drug formulation. Dose proportionality in plasma PK parameters (Cmax and AUCs) will be assessed graphically for Day 1 and Day 16 plasma concentrations for each formulation. Additional analyses will be included if appropriate.

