5.4 Study Design

The study is a investigator and subject blinded, sponsor-unblinded, placebo-controlled clinical study progressively assessing independent cohorts of healthy subjects to continue evaluation of the safety, tolerability, PK of escalating single doses (SD) and multiple doses (MD) of TAK-831, as either a suspension or T2 tablet formulation, at levels higher than those achieved in the initial single and multiple rising dose (SRD/MRD) Study TAK-831-1001.

Up to 6 cohorts will be run either singly or in parallel as non- cerebrospinal fluid (CSF) cohorts with plasma analysis or CSF cohorts with CSF analysis in addition to plasma analysis to assess TAK-831 exposure and CCI levels in the central nervous system (CNS). After meeting all the selection criteria, there will be 8 subjects enrolled in each cohort. They will be randomized on Day 1 in a ratio of 1:3 to receive placebo or TAK-831.

All cohorts will start with an initial, in-house SD period to include predose PD assessments on Day -1, Day 1 TAK-831 dosing, and a 48-hour in-house observation period with full PK/PD collections. The SD PK/PD collection and observation phase will be followed by 14 days of in-house MD.

In CSF cohorts, lumbar CSF samples will be collected through either a single lumbar puncture or an indwelling temporary catheter on 2 separate occasions. In CSF cohorts that use an indwelling temporary catheter on both occasions, the first collection will occur on Day 1, and the second on Day 16. In CSF cohorts where the predose CSF sample is collected through a single lumbar puncture, the first CSF sample will be collected on Day -1 prior to the start of CCI

monitoring and the second collection will be obtained through use of an indwelling temporary catheter on Day 16. If an indwelling temporary catheter is being used, it will collect serial CSF samples for 24 hours.

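### Dose proportionality is assessed with box plots and separate per-dose summaries, so the plan gives no between-dose estimate with its uncertainty; a descriptive slope and adjacent-dose ratios with 90% confidence intervals would supply one

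*SAP*

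**What the plan says.** Protocol 11.1.3 states that dose proportionality in plasma Cmax and AUCs "will be assessed graphically for Day 1 and Day 16 plasma concentrations for each formulation". SAP 8.9.1 keeps the graphical approach, names the plot and extends it to CSF: proportionality "will be assessed graphically using box-plots", by formulation, on Days 1 and 16, in plasma and in CSF. The plots cover both the raw and the dose-normalized parameters.

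SAP 8.9.1 also tabulates the PK parameters by dose and formulation (N, arithmetic mean, SD, %CV, median, minimum, maximum). Geometric means are added for Cmax and AUCs, "including those dose-normalized C_{max} and AUCs", and individual plasma parameters are listed. Other PK figures are left to a separate clinical pharmacology analysis plan, and the section closes with an open clause: "Additional analyses will be included if appropriate".

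Neither document names a slope, a ratio between doses, a confidence interval or a rule for reading the plots. SAP 7.0 gives 6 active and 2 placebo subjects per cohort and says that the number does not rest on power.

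**The concern.** Each box summarizes about six values. Six values per dose can look proportional, or not, by chance, and a plot carries no measure of how far chance alone could move it. The tables give one summary per dose and leave the reader to compare them without an interval.

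Plasma PK is the trial's secondary objective. Protocol 6.3.1 says that the study is meant to support dose selection for follow-up studies, and Protocol 11.2 allows preliminary analyses to inform dose selection for future development. For those uses, a statement about how exposure rises with dose is worth more with an estimate and its uncertainty attached. Without one, two readers of the same plots can reach different conclusions, and neither can say how well the data support them.

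**Working it through.** **Inputs from the documents**
- Active subjects: 6 per cohort (SAP 7.0). This agrees with the 1:3 allocation of 8 subjects (2 + 6), and 6 cohorts × 8 = 48 matches the planned total. There is no power-based figure to reproduce.
- Tablet T2 doses: 600 mg (Cohort 1) and 100 mg (Cohort 4). Suspension doses: 800 mg (Cohort 2) and 15 mg (Cohort 5). These are from Protocol 6.2 and Table 6.a. The table is broken in the text available for this review: the Cohort 3 suspension dose could not be read, and Cohort 6 is to be determined. Doses and dosing intervals may also change under Protocol 6.4.

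**Assumptions**
- Between-subject CV of 30% to 50%. The documents give no value.
- Lognormal parameters with the same variance at each dose.
- For the checks that need a third suspension level: 2000 mg, the ceiling in the footnote to Table 6.a.

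**Slope**

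Model: ln(parameter) = a + b·ln(dose), by formulation. On the log scale σ = √ln(1 + CV²), which is 0.294 at CV 30% and 0.472 at CV 50%. For two doses with n = 6 each, Sxx = 3·(ln r)², where r is the ratio of the higher to the lower dose. The 90% half-width is t(0.95, 10)·σ/√Sxx, with t = 1.812.

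| | r | ln r | √Sxx | SE, CV 30% / 50% | Half-width, CV 30% / 50% |
|---|---|---|---|---|---|
| Suspension 15, 800 mg | 53.3 | 3.98 | 6.89 | 0.043 / 0.069 | ±0.08 / ±0.12 |
| Tablet 100, 600 mg | 6 | 1.79 | 3.10 | 0.095 / 0.152 | ±0.17 / ±0.28 |

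Protocol 7.6 allows discontinued subjects to be "replaced to ensure that a minimum of 6 subjects are completed for each cohort". If both losses were active subjects, 4 would remain, and the tablet half-width would be ±0.23 to ±0.36.

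**The same interval on the exposure scale**

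With two doses, b = 1 + ln(R)/ln(r), where R is the ratio of dose-normalized geometric means. The interval for R is ×/÷ exp(t·σ·√(2/6)):
- CV 30%: exp(1.812 × 0.294 × 0.577) = 1.36
- CV 50%: exp(1.812 × 0.472 × 0.577) = 1.64

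The dose range cancels, so both formulations give the same factor. The suspension slope looks tighter only because the same log-scale error is divided by a larger ln r.

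As a yardstick (not one that the documents set), R would have to lie within 0.80 to 1.25. That needs t·σ·√(2/6) below ln 1.25 = 0.223, so σ below 0.213, or a CV below about 22%. In 20,000 simulated trials with true proportionality, the interval fell inside that region about 2% of the time at CV 30% and about 0% at CV 50%, for either formulation.

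**What one slope can hide**

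Suppose suspension exposure is proportional from 15 to 800 mg and completely flat from 800 to 2000 mg. With six subjects at each level, the fitted overall slope is still 0.87. The adjacent-dose ratio shows the plateau directly: the dose-normalized ratio of 2000 to 800 mg would be 800/2000 = 0.40. Its 90% interval would be about 0.29 to 0.54 at CV 30% (0.40 ×/÷ 1.36) and 0.24 to 0.66 at CV 50% (0.40 ×/÷ 1.64).

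**The case against.** The strongest reply is that the plan already holds most of the information. Dose-normalized geometric means are tabulated by dose and formulation, and with two doses the slope follows from their ratio, so the point estimate can be recovered. SD and %CV show the spread, and individual values are listed. The protocol and SAP agree with each other, dose proportionality is neither a stated objective nor a listed secondary endpoint, and further analyses are left open. This stands in part: a reader might infer that the plan offers no number at all, and the tables rule that out. What is missing is narrower, namely a prespecified contrast between doses with an interval. The open clause does not prespecify one, and the separate clinical pharmacology plan, which could not be seen, is cited only for figures.

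A reader might also infer that cohort escalation or the plateau rule suffers from the missing slope. The documents do not support that. Under Protocol 6.2, escalation is decided cohort by cohort during the trial by the sponsor and the principal investigator. Mean Cmax and AUC24 are compared with fixed limits, and the plateau criterion looks at the two highest dose cohorts. None of this waits for the final SAP table, and a single slope anchored at 15 mg could mask a plateau at the top. That objection stands, which is why the adjacent-dose ratios are needed beside the slope.

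**Conclusion.** The point holds as a minor, optional improvement. The plan names a graphical assessment and per-dose summaries, and no between-dose estimate with uncertainty.

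A reader might infer from the wide dose range that a power model would give a usefully narrow interval for each formulation. That is too strong. The suspension slope is narrow in slope units (±0.08 to ±0.12), the tablet slope is not (±0.17 to ±0.28), and both carry ×/÷1.36 to ×/÷1.64 on the dose-normalized ratio across the range. Neither could serve as proof of proportionality unless variability were well below the assumed range. With only two doses in a formulation, lack of fit cannot be checked.

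The benefit is a quantified dose-exposure relation for the PK objective and later dose selection. The sizes rest on the assumed CV, equal variance, 6 active subjects per dose, and dose levels that are partly unreadable, undetermined or open to change.

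**What to change.** Add to SAP 8.9.1, for plasma Cmax and AUCτ, by formulation and by day (1 and 16), as descriptive analyses with no pass/fail test:

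1. A power model, ln(parameter) = a + b·ln(dose per dosing interval), reporting b and its 90% confidence interval. Defining dose per dosing interval keeps the model usable if once-daily and twice-daily regimens are mixed.
2. Ratios of dose-normalized geometric means between adjacent dose levels, with 90% confidence intervals, because one slope can hide a plateau at the top doses.

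Keep the box plots. State that the tablet estimate is expected to be imprecise, that neither slope demonstrates proportionality, and that fit cannot be checked where a formulation has only two doses.

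Limit the addition to plasma. SAP Appendix E says that Cohorts 5 and 6 have no serial CSF collection on Day 1, so a Day 1 CSF slope from the 15 and 800 mg suspension cohorts could not be estimated.

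The cost is one table and a few lines of code. No new data are needed, and no dose or clinical rule changes.
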